### **3.2. ANALYSIS OF ETHICAL IMPLICATIONS**

This project has been formulated in response to both the international guidelines of the Council for International Organizations of Medical Sciences (CIOMS), an entity founded by UNESCO and WHO, whose great contribution has been the definition of guidelines for the application of ethical principles in several key areas of Health, and we have been particularly concerned to consider Chilean legislation and institutional frameworks.

All participation shall be preceded by the submission of information on: objectives, participation, procedures, benefits and foreseeable risks of the study. All participation will be formalized through the voluntary signing of an informed consent document by the participant. Throughout the study, the criteria of research integrity will be taken into account (Singapore Declaration).

A process of recruitment and selection of participants will be carried out through dissemination in educational establishments and through the ECO Network. In order to respect the autonomy of the subjects, participation will be completely voluntary and none of the instances of participation will include the registration or consultation of personal data.

#### **3.2.1. RISK-BENEFIT ANALYSIS**

We believe there are no potential risks in this study, physical, emotional, or otherwise. On the other hand, the results would allow for an intervention to improve CMH in children with PS, with its initial evidence on effectiveness and feasibility indicators, for its possible scaling up to the national level. Therefore, it is considered a study that has a favorable risk/benefit balance.

#### **3.2.2. SAFEGUARDING CONFIDENTIALITY**

For the purpose of the analysis and maintenance of databases, during the research process any information related to names, places or other data that could subsequently lead to the identification of the participants will be modified from the written and virtual records.

The lists of names and telephone numbers of the participants in the three stages will be maintained by the principal investigator in physical locations separate from the transcripts and audio and video recordings. While the transcripts and audio and video recordings will be stored in a computer with a key, which will be in a locked place and accessible only to researchers and therapists involved in the processes. The protocol for the data backup chain will be explicitly established, which, together with the informed consents, will be stored in a safe place, to which only the researchers in charge of the project will have access. The criteria of the Singapore Declaration on Integrity in Research will be taken into account. The project will take into account the criteria and recommendations of CONICYT and the Institutional Ethics Committee of the University of Valparaíso.

All transcripts of committee meetings and focus groups will be made by researchers, who will also participate in the data analysis process.

### **3.2.3. INFORMED CONSENT/ASSENT**

In the design of this study, the free, informed and consented participation of all research participants is contemplated. Each of these criteria is described below.

- a) Free participation: All participants will be informed of the objectives of the study and will have the freedom to agree to participate or not in the study, they will also be free to terminate their participation in the study at any time, without this generating any consequences.
- b) Informed participation: All participation will be preceded by the provision of information on objectives, type of participation, possible benefits and foreseeable risks of the study. Participants will also be informed about the characteristics of confidentiality and preservation of anonymity. They will also be informed about the methods of custody of the registered information, the uses that will be given to it and the treatment of said information for the purposes of publication of results.
- c) Consented participation: After having been informed about the research process, the participation of each person will be formalized through informed consent to participate, and to generate audiovisual material as a graphic record.

CONSENTS: During the first stage a committee will be constituted with the representatives of all the institutions, during the second stage the collection of the experience of the teachers and the invitation to the participatory construction of the mental health training program will be carried out, and finally in the final stage discussion groups will be made for the qualitative analysis DEXPLIS. Participants participating in any of the three stages must sign a prior informed consent. The consents will be applied online, since that will be the modality of participation, and thus the CEC-UV will be requested to approve the project.

In the event that any of the stages requires a graphic record of any activity, the express authorization of the participants will be requested.

ASSENTS: This project does not provide for the application of assets when there is no participation of underage subjects.

### **3.2.4. INSTITUTIONAL AUTHORIZATIONS REQUIRED**

In case of being awarded, the project will be evaluated by the Institutional Ethical-Scientific Committee of the University of Valparaíso [CEC-UV](#), which is accredited ([see payroll](#)).

### 3.3. WORK PLAN

Specific Objective	Activity	Months																							
		1	2	3	4	5	6	7	8	9	10	11	12	13	14	15	16	17	18	19	20	21	22	23	24
1-Build in a participatory way the contents of a Literacy program in CMH	1-Presentation of the Ethics Committee Project	x																							
	2- Random selection of the 4 PS		x																						
	3-Contact and invitation to working meetings of key informants of the territories and PS		x	x																					
	4- Establish work teams in each selected PS			x																					
	6- Participatory design of the literacy program			x	x	x	x																		
2. Implement the ECO-Barrio network strategy	1- Contact with key agents of the CMH network	x																							
	2-Form a committee in each sector with the representatives of the institutions of the intersectoral ecosystem in CMH	x																							
	3- Develop a participatory work plan with objectives, goals, activities, deadlines and managers.		x	x	x																				
	4-Bimonthly work and follow-up meetings.			x	x	x	x	x	x	x	x	x	x	x	x	x	x	x	x						
3. Assess whether the literacy program significantly improves knowledge in CMH	1- Recruitment of teachers to participate in the literacy intervention.			x	x	x	x																		
	2- Development of knowledge instrument in CMH			x																					
	3-Test of application of the instrument in PS of non-intervened sectors.				x																				
	4-Semantic adaptation of the instrument.					x																			
	5-Implementation of online literacy course (G1 and G2)							x	x	x	x	x	x	x	x	x	x	x	x						
	6 Evaluation of teachers intervened with instrument (pre and post intervention)							x					x							x					
4- Evaluate if the detection rate of CMH problems is significantly improved	1-Random selection of 2 PS similar to those selected in a neighborhood where the intervention has not been implemented				x																				
	2- Determine the detection rate in schools that received the literacy program compared to control schools												x										x		
5.Evaluate whether the relevance of referral to	1- Determine how many of the referred children enter Mental Health treatment (regardless of the device or level of complexity)						x	x	x	x	x	x	x	x	x	x	x	x	x						

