### **3. METHODOLOGY, ETHICS AND PLANNING**

#### **3.1. METHODOLOGY AND PROCEDURES**

Research design. This project corresponds to an evaluation of the preliminary effectiveness and feasibility of a multi-component pilot intervention. The program will be evaluated through a cluster randomized controlled trial (RCT)

The project activities are organized around two clearly defined stages: one of participatory construction, and another of evaluation of the effectiveness and feasibility of the pilot intervention. They are explained in detail below.

Effectiveness is studied through a mixed design (subtype DEXPLIS, explanatory design sequence), which begins with a quantitative study of quasi-experimental type (comparing equivalent intervention and control facilities) and is followed by a qualitative study to analyze the implementation process and results of the pilot to intervention(including its barriers and facilitators).

The reliability is studied through indicators of participation of teachers in the intervention (initial interest and retention over time), by the satisfaction of teachers and those who participate in the articulation of local health-education networks, and with the analysis of barriers and facilitators at all levels.

Universe and sample. The universe to which the results of this study could be extended are public educational establishments. For this study, two neighborhoods of the commune of Valparaíso were selected. Therefore, the selection of the territories is not random, but the selection of the 2 establishments in each territory is. The inclusion criteria are that they are public schools and have 1st to 8th levels of primary education. The list of establishments that exist in that sector and that meet the inclusion criteria will be taken and will be selected using some random method, 2 schools of each neighborhood (4 in total) will be initially assigned to the intervention and 2 will serve as a control (four in total). As previously described, in a second moment the intervention will be carried out in the establishments that served as control for ethical reasons.

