- a) Level of knowledge of the teachers, using an *ad hoc* questionnaire, which is built in the phase prior to the intervention and validated by this team (which incorporates teachers). The conceptual framework of literacy in child and adolescent mental health will be used. This questionnaire will include all the aspects that are part of the training program aimed at teachers and will allow them to obtain scores for their different modules or dimensions. A test and semantic adaptation will be carried out with teachers from establishments in other sectors of the commune, which do not participate in the project, prior to its use within the project. It is expected that in the initial assessment (baseline), the results will be similar in the teachers of the intervention and control establishments. At the end of the intervention it is expected that scores have improved significantly in intervention facilities and have not changed in control facilities.
- b) Rates of referral of mental health problems in children. In each project establishment (intervention and control) a centralized register will be kept of the children indicated by their teachers who require mental health care during the intervention. This will also allow for centralized coordination for referral to the relevant CESFAM. In this way the detection rate can be calculated.
- c) Waiting time between referral from the educational establishment to professional care at the corresponding CESFAM. This indicator is obtained from the centralized register in each educational establishment, which includes the date on which it coordinated with CESFAM for its attention, and the registration of the first attention in the latter. The time elapsed between the two is the waiting time that will be used as an indicator.
- d) Rate of accuracy for referral of children with suspected psychiatric disorders from the school to health care. Each “case” referral will apply the Strength and Difficulties Questionnaire (SDQ). 25 items (scale 0-2).

2) Evaluation of the feasibility of the intervention. Feasibility assessment uses a combination of quantitative (indicator) and qualitative methods, which are described below.

- a) Level of interest of teachers in the intervention: It is estimated through the percentage of teachers who agree to start the training course, out of the total number of teachers who were invited (which would be the totality of each educational establishment).

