###### **4.1.2. IMPLEMENTATION OF THE EXPECTED PRODUCT(S)**

The direct beneficiaries will be PS teachers from the commune of Valparaíso who receive basic education students and who voluntarily agree to participate in the child mental health literacy program. To this end, an e-learning platform will be developed with audiovisual resources for training in CMH, asynchronously, in addition to contemplating some synchronous meetings to resolve doubts with the participants of the training.

Additionally, training activities and facilitation of intersectoral coordination will be programmed for health, education, SENAME and other relevant actors, in order to support the process of identifying students who require mental health care in an opportune and pertinent manner, through the eco-neighborhood network that will be implemented in 2 sectors of Valparaíso. those that will be carried out online, given the current global health context, and taking advantage of the familiarity that has been given with these means that facilitate the meetings and reduce the expenditure of resources for their participants.

In relation to the e-learning platform, the project will remain as an input for CORMUVAL and the ECO-Barrio Network, so that they can continue using it in their activities.

Finally, the development of a critical nucleus and associativity of the University of Valparaíso with specialized groups is expected, which promotes more research in this area and constitutes updated and complementary information to what is currently available, in addition to contributing to the technological development of science solutions applied to public health in the area of child mental health. These expert groups have been described throughout the project.

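### Teachers volunteer for the course after the schools are selected, and no matching entry step, concealment or analysis set is described for control teachers, so randomising schools does not assure comparability on the knowledge outcome

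*Combined protocol and SAP*

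**What the plan says.** Section 3.1 (Methodology and procedures) describes a cluster randomised trial with the school as the allocated unit: "2 schools of each neighborhood (4 in total) will be initially assigned to the intervention and 2 will serve as a control", giving four control schools in all. Indicator 1a in that section is measured on teachers. It is the score on a purpose-built knowledge questionnaire, given before and after the course and compared between arms. It serves hypothesis 1 (section 2.3) and specific objective 3 (section 2.4.2). On the starting point the section says: "It is expected that in the initial assessment (baseline), the results will be similar in the teachers of the intervention and control establishments".

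The work plan (section 3.3) gives this order of events:

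- Month 2: "Random selection of the 4 PS". Four matches the number of intervention schools, but the row does not name the arm.
- Month 3: work teams are set up in each selected school.
- Months 3 to 6: "Recruitment of teachers to participate in the literacy intervention".
- Months 7, 12 and 19: knowledge tests. The row refers to teachers who received the intervention; no row covers testing of control teachers.
- Months 7 to 18: the online course, for two groups labelled G1 and G2, neither defined.

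Taking part is voluntary. Section 4.1.2 describes the beneficiaries as teachers "who voluntarily agree to participate in the child mental health literacy program", and section 5.4 says the same in substance. Feasibility indicator 2a (section 3.1) is the "percentage of teachers who agree to start the training course, out of the total number of teachers who were invited", with the whole staff of each school invited. No expected uptake is given.

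**The concern.** Randomising schools makes whole staffs comparable on average. It does not protect a subgroup of staff formed after allocation, unless that subgroup is formed in the same way in both arms. Here, entry in an intervention school may mean signing up for a certified course of three to four months (section 2.1) that starts soon. The plan describes no equivalent step for a control teacher.

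If those who sign up differ from their colleagues in knowledge, interest or speed of learning, the end-of-course contrast mixes the effect of the course with who chose to take it. The plan's expectation of similar baselines would then have no support from the randomisation. At stake is the answer to hypothesis 1.

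**Working it through.** **No figure to reproduce.** The plan gives no sample size, score SD or uptake for teachers. Its only sample size, 56 children per group, concerns the identification rate and does not bear on this point. The check is therefore a reading of the sections side by side, followed by an illustration under stated assumptions.

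**Who is compared.** Three readings fit the text:

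1. All teachers of each school are tested and compared by school allocation. Indicator 1a can be read this way, since it speaks of the teachers of the establishments.
2. Course volunteers are compared with whole control staffs. The testing row in section 3.3 points towards volunteers on the intervention side.
3. Volunteers are compared with volunteers, if G2 is the delayed group in control schools and the single recruitment row feeds both groups.

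No analysis set, baseline adjustment or concealment from teachers is stated, so the documents do not settle the choice.

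**Size under reading 2, the least favourable.** Let *u* be the share of staff who volunteer and *d* the volunteer minus non-volunteer difference in knowledge, in SD units. With non-volunteer mean *m*:

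- volunteers: *m* + *d*
- whole staff: *u*(*m* + *d*) + (1 − *u*)*m* = *m* + *ud*
- gap before any teaching, if control staff have the same make-up: *d* − *ud* = (1 − *u*)*d*

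Both *u* and *d* are assumptions.

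| Uptake *u* | 1 − *u* | gap at *d* = 0.2 | gap at *d* = 0.5 |
|---|---|---|---|
| 30% | 0.7 | 0.14 SD | 0.35 SD |
| 50% | 0.5 | 0.10 SD | 0.25 SD |
| 70% | 0.3 | 0.06 SD | 0.15 SD |
| 90% | 0.1 | 0.02 SD | 0.05 SD |
| 100% | 0 | 0 | 0 |

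The sign follows that of *d*. Keener teachers may know more, but teachers who feel poorly prepared may also be the ones who volunteer.

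**What the pre-test removes.** If the gap is constant over time, it appears in both the pre and the post contrast and cancels in a comparison of change. Adjusting for the baseline score removes the part that the score captures. Neither removes a difference in motivation or in rate of learning between those who sign up and those who do not. The documents offer nothing from which to size that remainder.

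**Reading 1** makes the selection gap nil. **Reading 3** leaves a smaller question: agreeing to a course now and agreeing to one later are different filters if teachers know which they are offered.

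**Timetable and control schools.** The recruitment and testing months above come from section 3.3. Section 3.1 places the pilot in months 12 to 24 and the control schools' course in months 18 to 24, while the course row in section 3.3 runs from month 7 to month 18. Section 3.3 also schedules, in month 4, "1-Random selection of 2 PS similar to those selected in a neighborhood where the intervention has not been implemented", against four control schools in the same territories in section 3.1. The two sections cannot both hold.

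**The case against.** The strongest reply is that the plan never says only volunteers will be analysed. It invites every teacher, words indicator 1a in terms of the teachers of each school, and tests before and after, so an imbalance in score would be seen and a stable one would cancel in a comparison of change. Control schools receive the course later, so their teachers may be recruited in the same window as G2. The outcome on which the study was sized, the detection rate, comes from a register kept in every school and does not depend on who takes the course if it is analysed by school.

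Much of this stands. It limits the point to indicator 1a and makes the table above a worst pairing rather than an estimate. It does not close the point. Inviting everyone does not prevent selection, because acceptance is what creates it. The readings that would remove or reduce the problem are possible but not written down.

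A reader might infer more: that the intervention teachers are not comparable with controls, that control teachers have no entry step, that volunteers know their arm, or that any bias favours the intervention. The documents do not support these as facts. G1 and G2 are undefined, the month 2 row names no arm, knowledge of allocation is an inference from being recruited to the course, and the direction depends on a sign that nobody has measured.

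**Conclusion.** The concern holds as a risk that the plan leaves open, not as a demonstrated imbalance. Teachers are recruited after the four schools are selected and before the first test. For control teachers no matching entry step is described, and neither concealment nor an analysis set is stated. For the knowledge outcome, the randomisation of schools therefore does not by itself assure comparable groups.

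The size is unknown. The range of 0.14 to 0.35 SD at 30% uptake and 0.10 to 0.25 SD at 50% rests on three assumptions: volunteers only in one arm, all staff in the other, and a volunteer difference of 0.2 to 0.5 SD in either direction. It refers to the baseline gap, part or all of which a change or baseline-adjusted analysis would remove. It is worth settling before recruitment, since the way teachers entered cannot be altered afterwards.

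**What to change.** First reconcile section 3.1 with section 3.3 on the number and location of control schools and on course timing, and define G1 and G2. Then:

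- Send the same invitation to all teachers in all intervention and control schools, stating that the course starts now or later depending on the school. This is true in both arms because controls receive the course.
- Record acceptance and give the baseline test before start dates are disclosed to staff, where feasible.
- Define the indicator 1a population identically in both arms: either all who accepted, whether or not they finish, or all teaching staff. Testing all staff removes this selection by design but means testing teachers who declined the course.
- Analyse by school allocation, allowing for clustering and adjusting for baseline score.
- Keep feasibility indicator 2a as the share who start the course among those invited, so that accepting a now-or-later offer does not replace it.

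With acceptors as the population, the cost is a reworded invitation and a sign-up step in control schools, with no testing beyond the pre and post tests already intended. The downsides are that control teachers will know a course is coming, and that staff in schools hosting design teams from month 3 may guess their start date.

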A two-year project is proposed, to be developed in four EEPs in Valparaíso. During the first 12 months, we will work on the construction of the literacy intervention with key actors of each establishment defining objectives, methodology and scope of the program, and then build the online platform with videotaped educational capsules. The network of children's MH or "ECO-Barrio Network" will be articulated with the local agents of the network (Local Public Education Service, National Service for Minors, Valparaíso-San Antonio Health Service, Municipality of Valparaíso and Primary Health Care other sectors involved). In the following 12 months, the literacy intervention will be applied in 4 of the 8 schools recruited, so that the other 4 schools will remain as a control. Finally, the intervention will be applied in the four schools that did not previously participate in the program. The results will be evaluated with indicators of acceptability, feasibility and effect in terms of achieving a better knowledge of the faculty about CMH, a pertinent and timely investigation of mental health studies at the school level and reduction of waiting times for care in the health and child protection system.

The results of this study will allow us to obtain the necessary information to design a larger study to evaluate the effectiveness and external validity of this multicomponent intervention.

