## **2. SOLUTION AND RESEARCH**

### **2.1. PROPOSED SOLUTION AND APPLICABILITY SCENARIOS**

This proposal seeks to build "school communities" based on Public Schools (PS), aimed at promoting MH in children and their families and detecting early MH problems in students, providing them with initial support and subsequent coordinated referral to treatment.

To achieve this, it is proposed to construct a participatory multicomponent intervention aimed at promoting the MH of children attending basic education in. The components of this grant are: 1) a Child Mental Health (CMH) Literacy program for PS teachers, which will be built in a participatory manner with them and other key actors; and, 2) the articulation of the local network of care in child and adolescent mental health, including several levels of complexity (community, primary care and specialized care) and, which occupies the strategy ECO-BARRIO SOLIDARIO with adaptations according to the new socio-sanitary context. Given the nature of a pilot project that, in the first instance, seeks to evaluate the feasibility of this intervention, its implementation is proposed in two neighborhoods of Valparaíso, with a random selection of 8 PS with primary education in each of

these neighborhoods, after the implementation of the program, the initial effectiveness of the literacy component in CMH will be evaluated with the teachers.

The process of participatory construction of the Literacy program in CMH will be developed during the first 12 months of the project, for which we will work with representatives of the academic body of these EEPs (teachers, parateachers, directors and others), parents, students, directors of the Local Education Service (SLEP) of Valparaíso and representatives of the ECO-Barrio network.

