To calculate the necessary sample size, the following parameters were considered: a prevalence of mental disorders of 27.8% and an identification rate of 30% of these cases (9 cases per 100 children, per year). This indicator (which corresponds to scenario 2 and specific objective 4) was taken as one of the most important achievements and reflects the impact of the intervention as a whole. To accept the fulfillment of our hypothesis, it will be necessary to double the identification rate to 60% of cases (18 cases per 100 children, per year). In this way, it is a comparison of proportions, where:  $p_1 = 0.3$ ,  $p_2 = 0.6$ , a confidence level of 95% for a unilateral test and a power level of 90%, 56 children are needed in each group. However, it is expected to work with a much larger sample: if it is considered that in each establishment there are 30 children per grade and only one course per level (from 1st to 8th grade). This would lead us to a potential sample of 240 children per establishment, which implies 480 in intervention facilities and 480 in control facilities.

Development of fieldwork. The development of the fieldwork has three fundamental stages: 1) Implementation of the ECO-Neighborhood Network strategy in the 1 selected neighborhood, (months 1

to 18), 2) the participatory construction of the components of the intervention (months 12 months); and 3) pilot-level evaluation of this intervention (months 12-24).

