3. The third part (months 12 to 24) consists of carrying out a pilot test taking 4 educational establishments located in two different territories of the commune of Valparaíso, in which the intervention will be carried out, and its results will be compared with 4 other equivalent educational establishments, from those same territories, which serve as control. Pre- and post-intervention assessments will be carried out, using a children's mental health knowledge survey, while referrals from facilities to the corresponding CESFAM will be recorded. Results will be compared between intervention and control results. Information is also collected to assess the participation of teachers in the intervention (feasibility analysis).

At the end of the intervention in the establishments that were the object of it, the quantitative indicators and results that were collected will be synthesized, and a qualitative analysis will be carried out (DEXPLIS design), based on discussion groups that involve the interested parties (teachers, mental health professionals and managers of both sectors). in which the results and achievements will be analyzed, barriers and facilitators of the process will be established, all of which will allow to complete the evaluation in a participatory way and to improve the components of the intervention, based on the empirical experience carried out.

After the end of the intervention, the intervention will also be carried out in its two components (teachers and health-education network) in the 4 establishments that served as control. In this way, an ethical requirement of not depriving the rest of the participants of a beneficial intervention is met. (Months 18 to 24)

Indicators, instruments and analysis procedures. For the detailed description of this point, the effectiveness analysis and the feasibility analysis of the pilot intervention are separated.

1) Evaluation of the effectiveness of the intervention. The effectiveness evaluation is based on comparing the following indicators between intervention and control establishments.

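### The work plan draws objective 4 control schools from an untreated neighbourhood, while section 3.1 assigns schools within the same two neighbourhoods; school numbers and network coverage also disagree

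*Combined protocol and SAP*

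**What the plan says.** **Source of controls.** Section 3.1 (universe and sample) says that "2 schools of each neighborhood (4 in total) will be initially assigned to the intervention and 2 will serve as a control", which makes four and four over two neighbourhoods. The third part of the fieldwork in the same section compares the intervention schools with "4 other equivalent educational establishments, from those same territories, which serve as control". The work plan in section 3.3 differs. Under objective 1 it selects 4 schools in month 2. Under objective 4 it schedules for month 4: "Random selection of 2 PS similar to those selected in a neighborhood where the intervention has not been implemented".

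**Design label.** Section 3.1 first calls the evaluation a cluster randomised controlled trial. Two paragraphs later it says that the mixed design "begins with a quantitative study of quasi-experimental type (comparing equivalent intervention and control facilities".

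**School numbers.** The Summary says that "the literacy intervention will be applied in 4 of the 8 schools recruited". Section 2.1 speaks of a "random selection of 8 PS with primary education in each of" the neighbourhoods. The sample size paragraph of section 3.1 ends with "480 in intervention facilities and 480 in control facilities".

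**Network coverage.** The network runs in one neighbourhood according to the start of the network paragraph in section 2.1 and the fieldwork paragraph of section 3.1. It runs in two according to the Summary, specific objective 2, section 4.1.2 and the end of that same paragraph in section 2.1.

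**The concern.** A control school cannot come both from the territories that receive the intervention and from a territory that does not. The two texts lead to different studies.

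Under section 3.1, chance decides which of the schools in a neighbourhood is treated first. Neighbourhood differences in case mix, health centre capacity or referral habits then fall on both arms.

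Under section 3.3, the intervention schools are drawn first and the controls are drawn two months later from somewhere else, chosen to be similar. Drawing schools at random from a list is random sampling. It does not randomise schools between arms, and arm and neighbourhood then move together.

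The conflict falls on the outcome that the sample size paragraph uses and treats as reflecting the intervention as a whole. The work plan is also the dated, operational schedule, so field staff could well follow it. Once schools have been chosen that way, no analysis can restore the allocation.

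**Working it through.** **1. The plan's own figure.** Inputs from the sample size paragraph of section 3.1: 30 children per grade, 8 grades, one class per grade.

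- Children per school: 30 × 8 = 240.
- Schools implied by the stated arm size: 480 / 240 = 2 per arm. The figure of 480 is reproduced only with 2 schools per arm.
- With the 4 schools per arm stated elsewhere in section 3.1: 4 × 240 = 960 per arm.

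**2. Layouts side by side.**

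| Place | Intervention + control schools | Children |
|---|---|---|
| Summary | 4 + 4 (8 recruited) | 960 v 960 |
| 2.1, read literally | 8 per neighbourhood, 16 in all | not stated |
| 3.1, universe and sample; third part | 4 + 4, same neighbourhoods | 960 v 960 |
| 3.1, sample size | 2 + 2 (implied) | 480 v 480 |
| 3.3, work plan | 4, then 2 from elsewhere | 960 v 480 |

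**3. What location does to the contrast.** Let τ be the between-neighbourhood standard deviation (SD) of the annual detection rate.

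- Section 3.1: each neighbourhood contributes equally to both arms, so τ cancels from the difference.
- Section 3.3, intervention schools in two neighbourhoods and controls in a third: the variance of the difference gains τ²(1/2 + 1) = 1.5τ².
- One neighbourhood against one: it gains 2τ².

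More pupils or more schools in the same places do not reduce these terms. The documents give no τ. For illustration only, assume a coefficient of variation of 0.2 (range 0.1 to 0.3) on the plan's control rate of 9 per 100 per year:

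- 9 × 0.2 × √1.5 = 2.2 per 100 (1.1 to 3.3)
- 9 × 0.2 × √2 = 2.5 per 100 (1.3 to 3.8)

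The target difference is 18 − 9 = 9 per 100.

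**4. What the number of schools does.** The smallest one-sided p-value of a randomisation test is 1 divided by the number of possible allocations.

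- 2 v 2, unrestricted: 1/C(4,2) = 1/6 = 0.167.
- 4 v 4, stratified by neighbourhood: 1/C(4,2)² = 1/36 = 0.028.
- Work plan layout: no randomisation between arms, so no such test exists.

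An illustration of power for the two randomised layouts uses 9 v 18 per 100, 240 children per school, one-sided 5%, and a noncentral t with 2(k − 1) degrees of freedom for k schools per arm. The squared standard error is [0.09 × 0.91 + 0.18 × 0.82] × (1 + 239 × ICC) / (240k). The intracluster correlation (ICC) is assumed.

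| ICC | 2 per arm | 4 per arm |
|---|---|---|
| 0 | 82% | about 100% |
| 0.01 | 44% | 87% |
| 0.02 | 32% | 69% |
| 0.05 | 20% | 42% |

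These figures take a full year of counting, an immediate effect and no contamination. They compare layouts and do not forecast the power of this study.

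**5. Why network coverage matters here.** If the network runs in only one of the two study neighbourhoods, the untreated neighbourhood in the work plan could be the second study neighbourhood. If it runs in both, it must be a third one. The documents do not settle which is meant.

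**The case against.** **Leftover or loosely translated text.** The 2 control schools of the work plan and the 480 per arm could both be remnants of a smaller design, and the 8 schools in each neighbourhood of section 2.1 may mean 8 in total. That is plausible, but all of it is current text. No such reading reconciles the work plan with section 3.1, or 480 with 960.

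**It is a pilot.** Section 3.1 does describe an "evaluation of the preliminary effectiveness and feasibility of a multi-component pilot intervention". This limits what may be claimed from objective 4, and an estimate with its interval is the right ambition. A pilot described as a cluster randomised trial still needs a single allocation scheme.

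**Controls from elsewhere avoid contamination.** This is the best argument for the work plan. The network works by sector, and section 3.1 gives control schools the same central register and referral coordination. The point stands as a cost of the fix. It does not make a comparison confounded with location a randomised one.

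**Stronger readings that the documents do not support.**

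- A reader might put a figure on the inflation of the false-positive rate under the work plan. Any such figure depends on an assumed ICC and neighbourhood variance, so it cannot carry the point.
- A reader might conclude that the randomised contrast is only the literacy component. Section 2.1 says that this component is evaluated with the teachers, which fits objective 3. For detection, the sample size paragraph refers to the whole intervention, and section 3.1 later gives both components to the control schools.
- A reader might infer from the month-22 mark in the work plan that treated controls are counted as controls. Section 3.1 keeps the register during the intervention and describes the synthesis of results before the control roll-out. The work plan table is also incomplete in the copy available. This is a matter for clarification only.

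**Conclusion.** The point holds: the plan as written contains two incompatible designs for objective 4, and this must be resolved before schools are selected. Section 3.1 gives a randomised comparison within neighbourhoods. Section 3.3, if followed, gives a non-randomised one in which arm is confounded with neighbourhood. The documents do not show that the study will be non-randomised; they show that it depends on which section staff follow.

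The arm size is also wrong by a factor of two for the stated 4 v 4 design (480 against 960), and the statements on network coverage contradict each other. These conclusions need no assumption beyond the plan's own 240 children per school. The neighbourhood SDs and powers shown above rest on assumed values and do not bear on the severity.

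**What to change.** 1. **One allocation scheme.** Keep the section 3.1 design. Replace the month-2 and month-4 selection rows of section 3.3 with one draw of 4 eligible schools per neighbourhood, randomised 2 v 2 within each at the same time. Delete the untreated-neighbourhood row and the quasi-experimental label. Correct the sample size paragraph to 960 per arm, and make the Summary, 2.1 and 3.3 agree on 8 schools, 4 v 4.
2. **Network and contrast.** Reconcile the coverage statements. The sponsor should state whether the objective 4 contrast is the whole intervention or the literacy component. Record any network activity that reaches control schools before roll-out.
3. **Analysis.** Compare school-level detection rates stratified by neighbourhood (8 schools − 2 strata − 1 arm term = 5 degrees of freedom). Report a preliminary estimate with its interval.
4. **Clarification.** State whether the month-12 or the month-22 detection count is the randomised comparison, given control roll-out in months 18 to 24.

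**Cost.** Protocol wording only: the Summary and section 3.1 already plan 8 schools. The plan does not say how many eligible schools each neighbourhood has, so confirm that there are at least 4 in each. The real price is that same-territory controls may be partly exposed to the network, which biases the contrast toward no difference. That is why the exposure should be recorded.
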